APPENDIX - Chronogram

## 1. Sinopse

Title:	Impact of AZathioprine in maintaining clinical, BIOmarkers and endoscopic remission among new pediatric patients with Crohn's disease treated with exclusive polymeric diet for induction of remission: a 2-year longitudinal analysis from the GEDII Registry – P-BIOAZA
	P-BIOAZA
Scientific Coordinator:	[name]
Disease/Condition	Crohn's disease
Rational	
Thus far, there is limited data on the impact of azathioprine in maintaining fecal calprotectin remission in CD patients.
 
Taking advantage of the valuable tool such as the GEDII Registry, the GEDII promoted a research to investigate the clinical, biomarker and endoscopic outcomes among patients with Crohn's disease and managed with azathioprine in the real-world practice. This study will follow a cohort of pediatric patients with Crohn's disease registered in the GEDII Registry who have induced remission with exclusive polymeric diet and who did initiate azathioprine at diagnosis based on physician's criteria. The cohort will be followed for a period of 2 years.
 
The primary aim of this study is to explore the potential value of azathioprine in maintaining fecal calprotectin remission in pediatric patients with CD.

Research hypothesis:	We hypothesize that pediatric Crohn's disease patients treated with exclusive polymeric diet and with azathioprine at the diagnosis will achieve and maintain fecal calprotectin remission.
Primary Objectives:	
Among patients with Crohn's disease at study inclusion, registered in the GEDII Registry:
 
 
•To evaluate the impact of azathioprine in inducing calprotectin remission (calprotectin levels < 200 ug/g) at week 12.
 
•To evaluate the impact of azathioprine in maintaining calprotectin remission (calprotectin levels < 200 ug/g) at week 48 and 96
 
•To evaluate the impact of azathioprine in maintaining calprotectin remission throughout a follow up period of 96 weeks.
 

Secondary Objective(s):	
 
•To explore the association of the fecal calprotectin assessment regarding clinical and endoscopic outcomes.
 
•To explore the association of fecal calprotectin levels with clinical outcome throughout a follow up period of 96 weeks.
 
•To explore the association of fecal calprotectin levels with endoscopic activity throughout a follow up period of 96 weeks.
 
•To evaluate the impact of azathioprine in inducing clinical remission at week 12.
 
•Among patients who achieve clinical remission with azathioprine, to evaluate the maintenance of clinical remission up to week 96.
 
•To evaluate the impact of azathioprine in inducing endoscopic remission at week 96.
 
•To evaluate the impact of azathioprine in maintaining endoscopic remission throughout a follow up period of 96 weeks.
 
•To evaluate the rate of azathioprine persistence throughout a follow up period of 96 weeks
 

	
 
•To evaluate the time until loss clinical remission
 

Study Design:	
Multicenter, prospective, observational study designed to gather and analyze data on a consecutive cohort of subjects with CD who initiated therapy with azathioprine, according to physician's clinical decision. There is no imposed experimental intervention and prescribing decisions from the study physicians will be independent of patient's participation in this study.
 
The maximum overall duration of observation for each patient is 96 weeks since the start of observation period (Day 1).

Inclusion Criteria:	
Study patients must fulfill the following criteria:
 
 
1. Male or female patients, <18 years;
 
2. Patients who are registered in the GEDII Registry;
 
3. Patients who have been treated with exclusive polymeric diet and start azathioprine at diagnosis
 
 
AND who meet one of the following:
 
 
o Moderate/Severe disease (PCDAI>31) at start of study with fecal calprotectin levels > 100 ug/g
 
o Mild disease (PCDAI>11<30) with fecal calprotectin levels > 100 ug/g and/or Endoscopic activity (Simple endoscopic score for Crohn's disease [SES-CD] ≥ 3)
 
 
 
4. Patients who gave their informed consent.
 

Exclusion Criteria:	
Patients will be excluded if at least one of the following criteria is met:
 
 
1. Patients on methotrexate or under biologics.
 
2. Any contraindications regarding the use of azathioprine;
 
3. Patients who are being treated with any investigational agent;
 
4. Patients who are not willing to comply with routine clinical appointments.
 

Expected number of patients:	80 patients
Expected number of sites:	Approximately 11 centers are expected to participate.
Subject selection:	The study will analyze a consecutive sample of 80 patients who are registered in the GEDII Registry and who fulfill the protocol's eligibility criteria. The recruitment period is 12 months but may be extended if the target number of participants is not achieved within the defined timeframe.
Exposure of interest:	Azathioprine is the exposure of interest. This medication may be tailored or optimized according to the physician's clinical criteria and taking in to account the label of the product.
Main data collected:	Socio-demographic, clinical and endoscopic data and patterns of use of azathioprine and other therapies for CD will be collected during the observation period, as well as PCDAI. The data collection time points in this study will reflect the routine schedule for CD patients receiving polymeric diet and azathioprine. The stool samples for assessment of fecal calprotectin will be collected by the patient at home, at the data collection time points.
Endpoints	
Primary endpoints:
 
 
•Proportion of patients who achieve fecal calprotectin remission (< 200 ug/g) at week 12.
 
•Proportion of patients who maintain fecal calprotectin remission (< 200 ug/g) at week 48 and 96.
 
•Proportion of patients who maintain fecal calprotectin remission (< 200 ug/g) at each data collection time point up to week 96.
 
 
Secondary endpoints:
 
 
•Fecal calprotectin levels assessed at each data collection time point.
 
•Fecal calprotectin levels and clinical activity (PCDAI) at each data collection time
 

	
point.
 
 
•Fecal calprotectin levels and endoscopic activity (Simple endoscopic score for Crohn's disease [SES-CD]) at week 96.
 
•Proportion of patients with clinical remission (PCDAI <math>\leq</math> 10) at each data collection time up to week 96.
 
•Proportion of patients who achieve endoscopic remission (SES-CD <math>\leq</math> 2) at week 96.
 
 
Among patients with moderate/severe CD (at inclusion) and who maintain clinical remission with azathioprine:
 
 
•Median time to loss of clinical remission (PCDAI>11) with azathioprine
 
 
Among patients with mild Crohn's disease at study inclusion and who maintain clinical remission with azathioprine:
 
 
•Median time to loss of clinical remission (PCDAI>11) with azathioprine
 
•Physician reported clinical outcome (PCDAI) at each data collection time points.
 

Statistical methods	
The association between two quantitative variables will be performed through Pearson correlation coefficient or Spearman correlation coefficient, in case the normality assumption is not verified. The association of two categorical variables will be tested through the Chi-Square test or Fisher Exact test (if applicable).
 
The comparison of two independent samples in respect to quantitative variables will be performed through t-test for independent samples or the Mann-Whitney non-parametric test, according to the assumption validations of the statistical test (if applicable).
 
The proportion of patients with clinical (PCDAI), and endoscopic remission (SES-CD) and biomarker remission (fecal calprotectin < 200 ug/g) at each data collection time points will be summarized using 95% confidence intervals, for the overall population and for the subset of patients with active and non-active CD at study inclusion.
 
Results for hemoglobin, leukocytes, neutrophils, eosinophiles, basophiles, monocytes, lymphocytes, erythrocyte sedimentation rate, CRP, ferritin, iron, transferrin and fecal calprotectin, will be summarized by total number of observations (n), mean, median, standard deviation, minimum and maximum.
 
The correlation between fecal calprotectin levels with clinical (PCDAI score) and endoscopic (SES-CD) activity of disease will be analyzed through the Pearson or Spearman (in case the normality assumption is not verified) correlation coefficient at each data collection time point:
 
 
○ Fecal calprotectin levels will be correlated with PCDAI score – Day 1, week 8, and every 12 weeks up to week 96.
 
○ Fecal calprotectin levels will be correlated with Simple endoscopic score for Crohn's disease (SES-CD) – Day 1 and Week 96.
 
 
Generalized Estimated Equations will be used to investigate clinical and endoscopic remission (homogeneity) throughout data collection time points (time-effect) for each of the two subsets (patients with moderate/severe CD; patients with mild CD at Day 1).
 
It is expected that: patients will achieve clinical and endoscopic remission and will maintain the remission up to week 96.

Overall Study Duration:	The overall duration of the study is approximately three years (1 year of recruitment + 2-year observation period).
Study timelines:	The study is expected to start during the 2 nd Quarter of 2016. Study closure is expected to occur 3 th Quarter of 2019.

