Thiopurines such as azathioprine has also been associated with mucosal healing in Crohn's disease. In children the effects of azathioprine on mucosal healing and histologic remission has been insufficiently studied until present. Studies in adults have shown different rates of mucosal healing; Mantarazis et al. found mucosal healing in 58% of patients while in SONIC study only 16,5% of patients on monotherapy with azathioprine achieved mucosal healing. Sandborn et al. (1995) evaluated the effect of intravenous loading doses of azathioprine. Six patients with inflammatory CD with both clinically and endoscopically active disease were included at study entry. After 16 weeks of treatment, of the four who achieved clinical remission all had endoscopic improvement and three had complete endoscopic healing. In the postoperative setting, D'Haens et al. (1997) showed that among patients with severe postoperative recurrence of steroid-refractory ileal disease, treatment with azathioprine for at least 6 months resulted in healing of severe lesions. Of the patients who achieved clinical remission 6 of 15 (40%) achieved complete mucosal healing of their ileum. Subtotal mucosal healing was achieved in 5 (33%) and partial healing was achieved in 3 (20%).

In children, as in adult patients, endoscopy is mandatory for the confirmation of the diagnosis of inflammatory bowel disease. Recent literature address the importance of repeat endoscopy for the management of pediatric inflammatory bowel disease. Thakkar et al. have shown an overall rate of management change after endoscopy evaluation in children with inflammatory bowel disease in approximately 42%, with addition of a new medication been the most common intervention.

The performance of endoscopic re-evaluation in the adequate time can contribute to the improvement of disease control allowing a best individualized tailored treatment.

Thus far, there is limited data on the impact of azathioprine in maintaining fecal calprotectin remission in CD patients.

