## 2.2 FAECAL CALPROTECTIN

Given the invasive nature of endoscopy, the implementation of an easy, non-invasive method to support the pre-diagnostic screening and monitoring of disease activity is essential especially in children.

Fecal calprotectin has been shown to be useful in the diagnosis of IBD, correlates with mucosal disease activity and can help to predict response to treatment or relapse. In IBD, the presence of active gut inflammation is associated with migration of leucocytes, including neutrophils, to the gut mucosa. As a result the faecal stream contains increased levels of these inflammatory proteins including calprotectin. Faecal calprotectin has been shown to differentiate quiescent from active disease in both patients with CD and UC.

A meta-analysis including 30 prospective studies showed that the sensitivity and specificity of fecal calprotectin in diagnosing IBDs could reach up to 95% and 91%, respectively. Fecal calprotectin also showed to be a reliable surrogate marker of treatment response. Calprotectin levels decrease significantly after infliximab treatment for 12 weeks, and it correlates with endoscopic index of severity (CDEIS). Røseth et al. (2004) showed that fecal calprotectin levels correlated with endoscopic mucosal healing. A meta-analysis focusing on fecal calprotectin in IBD relapse showed that the sensitivity and specificity when predicting the relapse are 78% and 73%, separately.

Currently, there is limited data on the impact of fecal calprotectin as a marker of treatment response in children. A meta-analysis including 8 pediatric studies (six prospective and two retrospective) showed that pooled sensitivity and specificity for the diagnosis utility of fecal calprotectin during the investigation of suspected pediatric IBD were 0,978 (95%CI,0.947-0.996) and 0,682 (95%CI, 0.502-0.863). Hamalain et al show in 36 children that fecal calprotectin levels rapidly decreases by week 2 in one third of patients treated with infliximab. In a preliminary study Kolho et al measured fecal calprotectin level during the induction and maintenance treatment with infliximab in 76 pediatric patients and concluded that the long-term prognosis was related to the response to induction therapy and reflected in low fecal calprotectin values between weeks 2 and 6 and clinical remission.

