## 9 ENDPOINTS

### 9.1 PRIMARY ENDPOINT

- Proportion of patients who achieve fecal calprotectin remission (< 200 ug/g) at week 12.
- Proportion of patients who maintain fecal calprotectin remission (< 200 ug/g) at week 48 and 96.
- Proportion of patients who maintain fecal calprotectin remission (< 200 ug/g) at each data collection time point up to week 96.

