## **10.2 SAMPLE SIZE**

It is expected to analyze a total of 80 new patients. This sample size will allow the evaluation of the potential of fecal calprotectin in predicting the induction and maintenance of clinical and endoscopic remission in this population. Regarding the correlation analysis, with this sample size there is a power probability greater than 95% that the lower limit of a one-sided 95% confidence interval is higher than 0.50, if the observed correlation coefficient is at least 0.75.

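### As planned, the study does not assess whether calprotectin below 200 ug/g, the cut-off behind all three primary endpoints, identifies endoscopic remission

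*Protocol*

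**What the plan says.** Section 9.1 of the protocol lists three primary endpoints, all on the same cut-off. The first reads "Proportion of patients who achieve fecal calprotectin remission (< 200 ug/g) at week 12". The second applies the same limit to maintenance at weeks 48 and 96, and the third applies it at every scheduled visit through week 96.

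Section 9.3 defines clinical remission (on PCDAI) and endoscopic remission (SES-CD of 2 or less), each with a reference. It has no entry for calprotectin remission, and no source for 200 ug/g is given elsewhere. The calprotectin threshold in the entry criteria is a different one, above 100 ug/g.

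One secondary objective is "To explore the association of the fecal calprotectin assessment regarding clinical and endoscopic outcomes". The synopsis fixes the method: "The correlation between fecal calprotectin levels with clinical (PCDAI score) and endoscopic (SES-CD) activity of disease will be analyzed through the Pearson or Spearman". Section 10.1 repeats it and sets the SES-CD correlation at Day 1 and week 96. Both places also list a chi-square or Fisher test for two categorical variables, if applicable, without naming any pair.

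Section 10.2 says the sample size lets the study evaluate the potential of calprotectin to predict induction and maintenance of clinical and endoscopic remission. Its only calculation concerns a correlation. With 80 patients and a coefficient of at least 0.75, the power exceeds 95% that "the lower limit of a one-sided 95% confidence interval is higher than 0.50".

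**The concern.** The question in section 10.2 is about predicting a state that is present or absent. The method attached to it, there and in the synopsis and section 10.1, is a coefficient between a laboratory level and a score. That coefficient is the same whether remission is set at 50, 200 or 1000 ug/g, so it can neither support nor weaken the cut-off on which every primary endpoint depends.

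The protocol's two thresholds make this more pressing. A child with a value between 101 and 199 ug/g passes the calprotectin criterion for entry and is already below the remission cut-off on Day 1.

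At stake is how the primary proportions are read. A correlation that meets its target could be taken as backing for the 200 ug/g definition, although calprotectin remission and endoscopic remission may disagree in a sizeable share of patients. The report would contain no planned figure showing how large that share is.

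**Working it through.** **1. The plan's own figure (section 10.2).** Inputs: N = 80, correlation 0.75, lower bound 0.50, one-sided 95% interval. By Fisher's z:

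power = Φ[(atanh 0.75 − atanh 0.50) × √(80 − 3) − 1.645]
= Φ[(0.973 − 0.549) × 8.775 − 1.645]
= Φ(3.718 − 1.645) = Φ(2.07) ≈ 0.98.

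The figure reproduces: 98.1% by formula and 98.4% by simulation, consistent with the stated value above 95%. Neither 200 ug/g nor SES-CD of 2 or less enters the calculation.

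**2. Does the correlation depend on the cut-off?** In one simulated sample of 80, all calprotectin values were multiplied by 0.5, 1 and 2, which is equivalent to moving the cut-off.

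| Multiplier | Spearman | Pearson | Sensitivity at 200 | Specificity at 200 |
|---|---|---|---|---|
| 0.5 | 0.711 | 0.554 | 0.92 | 0.49 |
| 1 | 0.711 | 0.554 | 0.70 | 0.79 |
| 2 | 0.711 | 0.554 | 0.54 | 0.86 |

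The coefficients do not move, while the accuracy of the cut-off changes greatly.

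**3. How much disagreement fits the planned correlation?** Assumptions: bivariate normal underlying scores; a share p in endoscopic remission of 40% or 58%; a share b below 200 ug/g of 50%. The 58% is the higher of two adult mucosal healing rates in section 2.1. The 40% and 50% are not in the document and were chosen so that the two prevalences are close. With J the joint probability of both states, the share classified differently is p + b − 2J.

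| Correlation | p | b | J | Classified differently |
|---|---|---|---|---|
| 0.75 | 0.40 | 0.50 | 0.329 | 0.90 − 0.659 = 0.24 |
| 0.75 | 0.58 | 0.50 | 0.421 | 1.08 − 0.843 = 0.24 |
| 0.50 | 0.40 | 0.50 | 0.280 | 0.90 − 0.561 = 0.34 |
| 0.50 | 0.58 | 0.50 | 0.372 | 1.08 − 0.743 = 0.34 |

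Part of this comes from the unequal prevalences, which alone force |p − b|: 10 points at 40% and 8 points at 58%.

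**4. Would the generic categorical test fill the gap?** Take the last row with n = 80. The expected table is about 29.7, 16.7, 10.3 and 23.3. Chi-square is 8.7, p ≈ 0.003 (0.006 with continuity correction). The test would be clearly significant with a third of patients classified differently. It rejects independence and gives no estimate of accuracy.

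**5. What precision would a two-by-two table give?** Exact 95% intervals, with all 80 evaluable unless stated:

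- Half in endoscopic remission, 32/40 correct: 64% to 91%.
- 30% in remission: sensitivity 19/24, 58% to 93%; specificity 45/56, 68% to 90%.
- 16.5% in remission (about 13 of 80): sensitivity 10/13, 46% to 95%.
- Only 60 evaluable, half in remission, 24/30: 61% to 92%.

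**The case against.** The strongest defence is that the protocol keeps calprotectin remission apart from clinical and endoscopic remission and never equates them. Its secondary objectives are exploratory and speak of levels and activity, for which a correlation is a reasonable summary. Cross-tabulations could also appear in a statistical analysis plan that is not shown. Most of this stands. It does not dispose of the point, because section 10.2 goes further and claims evaluation of prediction of remission, and the protocol itself names the method for it. That is a mismatch in what is written, not a detail left for later.

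Four stronger readings are tempting and are not supported:

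- **That the study is unable to answer the question.** The chronogram schedules stool sample and colonoscopy together at Day 1 and at week 96 or discontinuation, and both cut-offs are defined. The data will exist; the analysis is not named.
- **That the primary proportions are invalid.** They remain proportions below a stated biomarker cut-off. What is missing is a planned link to endoscopic remission.
- **That disagreement could exceed half of patients.** Pairing the lower adult rate, "only 16,5% of patients on monotherapy with azathioprine achieved mucosal healing", with 70% below 200 ug/g gives 54% disagreement and a positive predictive value of 23% at a correlation of 0.75. The mismatch in prevalence produces these: at 0.999 they are still 53.5% and 24%. The planned separate proportions would expose such a gap.
- **That the accuracy quoted in section 2.2 can be carried over.** "the sensitivity and specificity when predicting the relapse are 78% and 73%, separately" concerns relapse, with no cut-off given, and not concurrent endoscopic remission at 200 ug/g.

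**Conclusion.** The point holds as a mismatch between purpose and method. The synopsis, section 10.1 and section 10.2 fix a correlation of levels with scores. That analysis does not assess whether calprotectin below 200 ug/g identifies SES-CD of 2 or less, and it does not measure prediction of remission as section 10.2 claims. The generic chi-square or Fisher line is tied to no pair of variables and yields no accuracy estimate.

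With near-matched prevalences, about 24% of patients would be classified differently at the hoped-for correlation of 0.75 and about 34% at 0.50. These sizes rest on the normal model and on assumed prevalences; they illustrate what the correlation leaves open and do not forecast the trial's result. The power statement is not wrong; it answers a different question.

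**What to change.** - **Synopsis and section 10.1:** prespecify, for week 96, the two-by-two table of calprotectin below 200 ug/g against SES-CD of 2 or less. Report sensitivity, specificity, and positive and negative predictive values with exact 95% confidence intervals. Add the ROC area for the calprotectin level as a supplement. Keep the Pearson or Spearman coefficients as supportive.
- **Section 10.2:** state that the power figure applies to the correlation only and not to prediction of remission.

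Accuracy tables against PCDAI at every one of the nine follow-up visits are not needed; they would add many imprecise estimates.

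The cost is one table from data already scheduled. The drawback is precision. About 13 points either side of the estimate requires some 40 patients in each endoscopic group, and sensitivity becomes very uncertain if few are in endoscopic remission or if week 96 colonoscopies or samples are missing. The result may look less favourable than a single coefficient, but it addresses the question that section 10.2 poses. Fixing it in advance also guards against choosing a cut-off after the data are seen.

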## 2 INTRODUCTION

### 2.1 CROHN'S DISEASE

Inflammatory bowel disease (IBD) is a chronic and disabling condition with an increasing incidence in southern Europe. The etiology of IBD remains unknown, but the characteristic disproportionate inflammatory response in the gut may develop through various mechanisms at the cellular and subcellular level. Ulcerative colitis (UC) and Crohn's disease (CD) represent the two main types of IBD.

In Portugal, the prevalence of IBDs increased from 86 to 146 persons per 100 000 inhabitants between 2003 and 2007. Within the same timeframe, the prevalence of UC and CD increased from 42 to 71 persons per 100 000 inhabitants and from 43 to 73 persons per 100 000 inhabitants, respectively. IBDs are more prevalent among women. The prevalence of Portuguese pediatric IBD is unknown. In the last years the incidence of pediatric Crohn's disease seems to be increasing for uncertain reasons in different parts of the world.

Crohn's disease is a relapsing, transmural inflammatory disease of the gastrointestinal mucosa that can affect the entire gastrointestinal tract from the mouth to the anus. Typical presentations include the discontinuous involvement of various portions of the gastrointestinal tract and the development of complications including strictures, abscesses, or fistulas.

Given the autoimmune nature of CD, many of the therapies used for this disorder are targeted to reduce the inflammatory response. There are several pharmacologic options available to patients with CD, and therapy is often best tailored to the level of disease severity. Therapies for mild disease are aimed at alleviating symptoms while also minimizing medication-related side effects. The two main classes of medications most often used for mild disease are 5-aminosalicylate (5-ASA) and budesonide. Both of these agents are designed to work at the mucosal level, with reduced systemic absorption and effects.

The initial therapy available for the acute management of CD has traditionally been systemic corticosteroids. Several early studies demonstrated the efficacy of corticosteroids in inducing remission in CD, with remission rates in up to 92% of patients. Despite the ability to induce remission, corticosteroids have not demonstrated equivalent efficacy at maintaining remission and are also known for relevant long-term side effects. Exclusive polymeric diet has a similar rate of induction of remission as corticosteroids and has no side effects. For that reason exclusive polymeric diet is considered the first line therapy to induce remission in children with active luminal disease usually in association with azathioprine for maintenance of remission. Thiopurines are recommended as one option for maintenance of steroid free remission in children at risk of poor disease outcome. Thiopurines alone are not recommended as induction therapy. When exclusive polymeric diet is not an option corticosteroids may be necessary. There are two main classes of corticosteroid-sparing agents and in moderate to severe CD: the immunomodulators, which include azathioprine (AZA), 6-mercaptopurine (6MP), and methotrexate (MTX), and the newer "biologics," monoclonal antibodies against TNF- $\alpha$ , which include infliximab, adalimumab, and certolizumab pegol. In addition, there has been recent evidence suggesting that combination therapy with an immunomodulator and biologic may be the most efficacious and may potentially alter the underlying prognosis of CD.

The thiopurines, which consist of AZA and 6MP, exert their effect via inhibition of purine synthesis. AZA is a prodrug, converted to 6MP within the host. AZA and 6MP dosing must be carefully titrated due to potential marrow-suppressive and hepatotoxic effects. The goal dose of AZA is typically

between 2 to 3 mg/kg/day, whereas the dose for 6MP is half this, at 1 to 1.5 mg/kg/d. As specific metabolites can lead to undesirable side effects, it is advisable to measure TPMT genotype or enzymatic activity prior to initiation of therapy. A rare TPMT genetic variant, for which ~0.3% of individuals are homozygous, can result in decreased TPMT function and elevated levels of 6-TG resulting in life-threatening marrow suppression. Approximately 11% of individuals are heterozygotes for this codominant mutation, requiring reduced dosing.

Two recent Cochrane analyses have synthesized the existing data regarding the efficacy of AZA and 6MP in the induction and maintenance of remission in CD. Prefontaine et al. (2010) assessed eight RCTs of AZA/6MP for induction of remission in 425 patients with active CD. Overall response in the pooled treatment group was 54 versus 33% in the placebo arm (odds ratio [OR], 2.43; 95% CI, 1.62-3.64). In addition to clinical response, five studies reported data on corticosteroid reduction while on these agents, with 76 of 117 (65%) thiopurine-treated patients exhibiting reduced steroid use, compared with 39 of 109 (39%) in the placebo group (OR, 3.69; 95% CI, 2.12-6.42). This meta-analysis was updated in 2013, showing that AZA and 6MP offer no advantage over placebo for induction of remission or clinical improvement in active Crohn's disease. However, the combination of AZA and infliximab was superior to infliximab alone for induction of steroid-free remission.

With respect to maintenance of remission, a recent systematic review assessing seven trials with AZA and one with 6MP demonstrated, among 550 adult patients, an OR of 2.32 (95% CI, 1.55-3.49) for AZA and 3.32 (95% CI, 1.40-7.87) for 6MP. A significant number of patients receiving AZA for maintenance of remission had to stop taking the medication due to intolerance, compared with placebo, with an OR of 3.74 (95% CI, 1.48-9.45).

Markowitz et al shown, in 55 children submitted to induction of remission with corticosteroids and randomized to receive 6MP or placebo at week 8, a 9% relapse in the group treated with 6 MP compared with 47% of the controls during a follow up period of 18 months. However subsequent observational studies have not been able to reproduce these low relapse rates, as relapse rates of 40 to 60% were found with azathioprine.

Thiopurines such as azathioprine has also been associated with mucosal healing in Crohn's disease. In children the effects of azathioprine on mucosal healing and histologic remission has been insufficiently studied until present. Studies in adults have shown different rates of mucosal healing; Mantarazis et al. found mucosal healing in 58% of patients while in SONIC study only 16,5% of patients on monotherapy with azathioprine achieved mucosal healing. Sandborn et al. (1995) evaluated the effect of intravenous loading doses of azathioprine. Six patients with inflammatory CD with both clinically and endoscopically active disease were included at study entry. After 16 weeks of treatment, of the four who achieved clinical remission all had endoscopic improvement and three had complete endoscopic healing. In the postoperative setting, D'Haens et al. (1997) showed that among patients with severe postoperative recurrence of steroid-refractory ileal disease, treatment with azathioprine for at least 6 months resulted in healing of severe lesions. Of the patients who achieved clinical remission 6 of 15 (40%) achieved complete mucosal healing of their ileum. Subtotal mucosal healing was achieved in 5 (33%) and partial healing was achieved in 3 (20%).

In children, as in adult patients, endoscopy is mandatory for the confirmation of the diagnosis of inflammatory bowel disease. Recent literature address the importance of repeat endoscopy for the management of pediatric inflammatory bowel disease. Thakkar et al. have shown an overall rate of management change after endoscopy evaluation in children with inflammatory bowel disease in approximately 42%, with addition of a new medication been the most common intervention.

The performance of endoscopic re-evaluation in the adequate time can contribute to the improvement of disease control allowing a best individualized tailored treatment.

Thus far, there is limited data on the impact of azathioprine in maintaining fecal calprotectin remission in CD patients.

